project enrolling a total of 300 subjects in both phases. These estimates are founded in the current literature and the analyses, hypotheses, and predictions of experts in the field.

[name]'s ongoing study (R01AA020836) comparing the effectiveness of oral naltrexone to XR-NTX in alcohol dependent primary care patients has a targeted enrollment of n=117 in each of the two arms to detect a 20% absolute difference in primary clinical outcomes based in the Fisher's exact test with a projected power of 90%. [name], PhDs' (R01 AA022309) four-arm RCT of alcohol dependent homeless individuals recruited from a community housing program (XR-NTX + Counseling, Placebo + Counseling, Counseling alone, Treatment as Usual) will enroll a total of 300 patients (N=75/arm). This study population is similar to the one we will be studying.

A sample of 125 subjects per arm would allow us to detect a moderate effect size (Cohen's d of slightly less than 0.40) to provide power of 0.80 or greater at  $\alpha < .05$ . Another consideration when determining sample size is to power the study to detect the reduction in ED visits that would entirely offset the cost of medication. The institutional costs of a dose of Vivitrol (XR-NTX) is comparable to the estimated institutional cost of a single ED visit to Bellevue Hospital (according to the New York State Institute Cost Review). To detect a difference of  $\geq 6$  ED visits (i.e. a 6 month course of Vivitrol) between study arms comprised of subjects having a mean of  $22 \pm 15$  ED visits per year (per our pilot study data), would require 100 subjects per arm with  $\alpha = 0.05$ ;  $\beta = 0.20$  or, more conservatively, 133 subjects per arm with  $\alpha = 0.05$  and  $\beta = 0.10$ .

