Research Assessments (Aim 2): We will collect demographic information and assess a broad range of subject characteristics using validated, reliable questionnaires and other instruments that are widely-used, including in ongoing XR-NTX studies, and for which trainings are available. Data collection at enrollment and months 3, 6, and 12 will include several outcome variables of interest that we have broadly classified as drinking metrics, healthcare utilization, and quality of life. The 30-day Timeline Follow-Back (TLFB) for heavy drinking days is the standard method for assessing self-reported alcohol consumption. The Economic Form 90 notably was used in the COMBINE study and is currently in use by in ongoing alcohol research for assessment of a broad range of health and public sector services utilization (including medical, self-help, legal services) and cost-effectiveness analyses. The Short Index of Problems Related to Alcohol (SIP-2R), and EuroQol-5D (EQ-5D) will be used for quality of life assessments. We will also conduct a 30-minute semi-structured qualitative interview and assess craving (Penn Alcohol Craving Scale), Self-Efficacy (Alcohol Abstinence Self-Efficacy Scale (AASE)), and Patient Motivation and Satisfaction scales. We will collect blood levels of carbohydrate deficient transferrin and GGT, which are biomarkers used together to objectively quantitate heavy drinking. We will ascertain healthcare utilization by triangulating data from Bellevue/HHC hospitals databases, EMS ambulance transports to all NYC EDs, Medicaid claims data, and subject self-report.

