We will collect patient-level characteristics data to explore the association of patient-level characteristics (e.g. sex, race) with effectiveness. We will be able to carefully track prior detox admissions and concurrent 12-step and specialty alcohol treatment involvement in the proposed trial in order to estimate associations with treatment effectiveness. Multivariate models will be used to identify patient characteristics associated with treatment success. The analysis will utilize a logistic regression with an indicator variable for treatment and covariate terms for baseline potential prognostic indicators, including African American ethnicity, baseline drinking severity, and status of housing, social support, quality of life, and OPRM1 genotype. Odds ratios will be calculated to quantify the risk to treatment failure of significant predictors. As originally proposed, naltrexone appears most effective at reducing heavy drinking, as opposed to producing complete abstinence. A harm reductionist perspective delineating treatment success from failure is particularly important in this population having a greater severity of AUD and psychosocial dysfunction. All traditional alcohol treatment trial clinical endpoints, including continuous

CONFIDENTIAL

This material is the property of the NYU School of Medicine and Langone Medical Center. Do not disclose or use except as authorized in writing by the study sponsor

drinking and heavy drinking variables, as well as the %CDT biomarker, the change in CDT, and the combined CDT-GGT equation, which are specific for heavy drinking, are of great interest, and will be reported.

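### Aim 3 specifies only a logistic model of an undefined success/failure outcome. A full-scale model of heavy drinking days should be added, because a cut of that count would cost precision.

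*Combined protocol and SAP*

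**What the plan says.** Section 7.2.2, Aim 3, announces multivariate models in general terms and then specifies one: "The analysis will utilize a logistic regression with an indicator variable for treatment and covariate terms for baseline potential prognostic indicators". Its output is on the odds scale: "Odds ratios will be calculated to quantify the risk to treatment failure of significant predictors". No threshold, time point or source variable defines success or failure. The reason given for the split is harm reduction: "A harm reductionist perspective delineating treatment success from failure is particularly important in this population". The same paragraph says that "naltrexone appears most effective at reducing heavy drinking, as opposed to producing complete abstinence".

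The paragraph closes by promising to report other endpoints: "All traditional alcohol treatment trial clinical endpoints, including continuous" (the sentence runs over a page break) "drinking and heavy drinking variables, as well as the %CDT biomarker, the change in CDT, and the combined CDT-GGT equation". No model is named for them.

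Section 7.2.1 describes the drinking measure: "The 30-day Timeline Follow-Back (TLFB) for heavy drinking days is the standard method for assessing self-reported alcohol consumption". It is collected at enrollment and at months 3, 6 and 12, so each subject can have a 0-30 day count at baseline and at follow-up.

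Section 7.1 gives a general phase 2 sensitivity figure on a continuous scale: "A sample of 125 subjects per arm would allow us to detect a moderate effect size (Cohen's d of slightly less than 0.40", for power of at least 0.80. It is not tied to heavy drinking days or to Aim 3. Aim 3 itself is described as exploratory and not powered for its hypotheses.

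**The concern.** Heavy drinking days are a graded outcome, and the plan expects a graded benefit. If success is a cut of that count, the logistic model uses only which side of the cut a subject falls on and discards how far drinking moved. The odds ratios would also depend on a threshold that the plan leaves open and that could be chosen after the data are seen.

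Sections 2 and 3.3 intend Aim 3 to inform treatment choice. An analysis that already has limited information has little to spare, so real associations would be estimated less precisely and missed more often.

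The Aim 2 text does not fill the gap. Its between-arm t or rank-sum tests are for pre-treatment variables, and its pre-post tests are within group. Its difference-in-differences regression is for healthcare use and expenditures, and the repeated-measures ANOVA under Aim 2c is for biomarkers. None of these relates predictors to heavy drinking days.

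**Working it through.** **Inputs from the documents.** 125 per arm, alpha 0.05, power of at least 0.80 and d slightly below 0.40 (section 7.1); 50 pilot subjects, taken as 25 per arm; a 0-30 day count (section 7.2.1).

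**Assumptions.** Two-sided test; success is a cut of the drinking outcome; standard-care success c between 10% and 50%; the section 7.1 effect size applies to this outcome. The plan gives none of these for Aim 3.

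**1. The plan's own figure.** Detectable d = (1.960 + 0.842) × √(2/125) = 0.354. Power = Φ(d√(n/2) − 1.96). At d = 0.355: Φ(2.807 − 1.96) = 0.801. At d = 0.40: Φ(3.162 − 1.96) = 0.885. Section 7.1 reproduces.

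**2. Treatment term after a cut, normal scale.** Treated success p = Φ(Φ⁻¹(c) + d). Power = Φ((Δ − 1.96·SE₀)/SE₁), with SE₀ pooled and SE₁ unpooled. This two-proportion test stands in for the logistic treatment term without covariates. Example, c = 0.10 and d = 0.355: p = 0.177, Δ = 0.077, SE₀ = 0.0437, SE₁ = 0.0434, so Φ(−0.197) = 0.422.

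| Standard-care success | Power, d = 0.355 (full scale 0.801) | Loss, points | Power, d = 0.40 (full scale 0.885) | Loss, points |
|---|---|---|---|---|
| 50% | 0.601 | 20.0 | 0.703 | 18.2 |
| 30% | 0.587 | 21.4 | 0.693 | 19.3 |
| 20% | 0.536 | 26.5 | 0.641 | 24.4 |
| 10% | 0.422 | 38.0 | 0.517 | 36.9 |

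At 5% success the loss is 49-50 points. A Wald log-odds calculation at d = 0.356 gives 0.416 to 0.604 for success of 10% to 50%, in agreement.

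**3. Bounded, skewed count.** Section 7.2.2 says several endpoints will not be normal, so 0-30 counts were simulated from assumed beta-binomial distributions (125 per arm, 3000 replicates, realised d 0.352 to 0.383) and a t-test was compared with cuts at 0, 2, 4, 8 and 15 days. Where 16-52% of controls succeeded, the loss ran from 10 points (0.853 to 0.751) to about 28 (0.794 to 0.519). Rarer success cost more: at 8% in one scenario, 0.780 fell to 0.374. A separate bounded-count simulation went from about 0.87 to 0.57-0.69, a loss of 18-30 points.

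**4. Predictor terms.** Same formulas, N = 250, d 0.355 to 0.40, and success of 10%, 30% or 50% among subjects without the predictor:

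| Predictor prevalence | Full-scale power | Loss, points |
|---|---|---|
| 40% | 0.785-0.873 | 19-36 |
| 25% | 0.681-0.782 | 19-32 |
| 10% | 0.391-0.475 | 11-17 |
| 5% | 0.231-0.280 | 4-11 |

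The documents give no predictor effect sizes. With a smaller d the losses shrink: at d = 0.20 and an even split, 11-19 points from a base of 0.352.

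**5. Pilot.** At 25 per arm full-scale power is 0.24 at d = 0.355 and 0.29 at d = 0.40. After a cut with 10-50% success it is 0.12 to 0.20, a loss of about 8-15 points.

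**The case against.** The strongest reply is that the premise is inferred. The plan never says that success is a cut of heavy drinking days. Effectiveness elsewhere in 7.2.2 also covers quality of life and consequences, so the loss cannot be sized without a definition. This stands as a limit on the numbers, which are conditional. It does not remove the gap: whatever success turns out to be, no predictor model uses the day count.

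Second, the plan promises to report continuous endpoints, and the Study Summary foresees changes in scores within and between groups. A reader might therefore infer too much from a claim that effectiveness is examined only as a dichotomy. That is correct: the logistic regression is the only regression specified for Aim 3, not the only treatment of drinking in the plan. Reporting an endpoint is still not the same as modelling its predictors.

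Third, Aim 3 is exploratory and declared unpowered, and the treatment effect on drinking belongs mainly to Aim 2. This stands. The consequence is lower precision, not a missed design target.

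Fourth, a reader might infer that the dichotomy contradicts the harm-reduction rationale, for instance because a fall from 28 to 12 heavy days would count as failure. That holds only for an absolute cut below 12. A cut at 15, or a reduction-from-baseline rule, would separate such a subject from one who did not change, and the plan excludes neither.

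Finally, questions of differential effectiveness need treatment-by-covariate terms. A full-scale model with main effects alone does not supply them; that is a separate matter.

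**Conclusion.** The point holds in conditional form. Aim 3 specifies a single regression, on an undefined success/failure outcome, and leaves a baseline-and-follow-up day count without a predictor model. If success is a cut of that count, precision is lost in every 125-per-arm scenario at the section 7.1 effect size. For the treatment term the loss is about 18-38 points under normality and about 10-30 points with bounded counts, for standard-care success of roughly 10-50% and 16-52% respectively, and more where success is rarer.

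The documents do not support attaching 18-38 points to the treatment term and its predictors without conditions. The effect size is borrowed from a general phase 2 figure, the cut and success rate are assumed, and predictor losses run from about 4 to 36 points by prevalence. At pilot size the loss is about 8-15 points from power below 0.30. No power stated in the plan is missed.

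**What to change.** In section 7.2.2, Aim 3, name as the main predictor model a regression of heavy drinking days on the full 0-30 scale at the month-6 and month-12 research visits. Use either a linear model with robust standard errors or a proportional-odds model, and state which. Include the treatment indicator, the covariates already listed and baseline heavy drinking days. Report each coefficient with a 95% confidence interval.

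Keep the logistic regression as the secondary harm-reduction summary, and define success before outcome data are examined: the variable, the threshold or change rule, and the visit.

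The cost is SAP wording and one additional model on data already being collected. The downside is small: effects read in days, or as common odds ratios, instead of odds ratios for success, and the bounded, skewed count rules out ordinary linear-model standard errors.

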02263. Cost assessment will be conceptually similar to recently published analyses of the COMBINE interventions and will include medical and non-medical costs as well as payer and societal costs (Form 90). Effectiveness assessment will include alcohol consumption measures, quality of life, consequences, and the EQ-5D. The EQ-5D is among the most commonly used quality-of-life measure for informing cost-effectiveness analyses because it has minimal respondent burden, is well validated, and it yields utilities (preference-based measures on a scale of 0 to 1), the desired input for cost-effectiveness models. Because costs are skewed, incremental costs will be assessed using ordinary least squares and median regression models with covariates for treatment intervention and other relevant factors, and conditional models may be used because of cost data that may include “zeros.”

**Figure 3: The Predictor variables (study arms) are shown on the left and four outcome domains on the right (Healthcare utilization, Drinking, Quality of Life, and Consequences) with the specific measures noted alongside each domain. The outcomes may be mediated by the subjects' development of engagement (assessed by AASE scale, motivation visual analogue scale, adherence to treatment arm, and participation in clinic). Several potential interactions are hypothesized, some of which may also act as confounders. Interactions or confounding may occur between outcome domains (e.g. quality of life may have an effect on healthcare utilization); other cofounders may include age, race, sex, socioeconomic status, comorbidities, and social stability. Randomization will be employed to help mitigate potential threats.**

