### **Aim 3: Patient-Level Predictors of Effectiveness:**

Baseline and longitudinal predictors of interest in naltrexone alcohol treatment efficacy and effectiveness trials include gender, ethnicity, mu opioid receptor genotype, and ancillary alcohol behavioral treatment involvement. Naltrexone's relative ineffectiveness in African American clinical trial sub-populations, including in the COMBINE trial, is possibly mediated by low rates of the Asp40 OPRM1 functional allele in persons of African descent, who are primarily Asn40 homozygous. This Asp40 (A118G, 'G' allele) OPRM1 functional single nucleotide polymorphism has been shown to be associated with successful treatment with naltrexone. A pilot conducted by [name] at Bellevue did find a strong association between persons involved at baseline or who became involved during primary care XR-NTX treatment with specialty alcohol treatment and/or Alcoholics Anonymous. Thus, we hypothesize a priori that there will be less robust effectiveness among African Americans; voluntary specialty alcohol treatment and Alcoholics Anonymous involvement, and presence of the Asp40 OPRM1 SNP will be associated with treatment effectiveness. We note, however, that these analyses will be exploratory, as the study is not powered to carefully test these secondary hypotheses.

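### The Aim 3 logistic model names no treatment-by-factor term, so it cannot estimate whether the XR-NTX+CM effect differs by African American ethnicity or, read as naltrexone response, by OPRM1 Asp40

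*Combined protocol and SAP*

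**What the plan says.** Section 7.2.2, Aim 3, states a directional hypothesis about ethnicity: "we hypothesize a priori that there will be less robust effectiveness among African Americans". The background given for it is that naltrexone performed comparatively poorly in African American participants of earlier trials. On genotype, the section expects that "presence of the Asp40 OPRM1 SNP will be associated with treatment effectiveness", and says of the allele that it "has been shown to be associated with successful treatment with naltrexone".

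The method follows: "Multivariate models will be used to identify patient characteristics associated with treatment success", by means of a "logistic regression with an indicator variable for treatment and covariate terms for baseline potential prognostic indicators". African American ethnicity and OPRM1 genotype both appear in the covariate list, beside baseline drinking severity, housing, social support and quality of life. The planned output is this: "Odds ratios will be calculated to quantify the risk to treatment failure of significant predictors". Section 7.3 analyses everyone randomized, in both arms.

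Interactions are raised only under Aim 2. The Figure 3 legend says "Several potential interactions are hypothesized, some of which may also act as confounders", and the example it words is between outcome domains. No model term is given there. Aim 3 carries the qualification that "these analyses will be exploratory, as the study is not powered to carefully test these secondary hypotheses". Sections 2 and 3.3 say the results are meant to guide the choice of treatment for individual patients.

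**The concern.** A smaller effect in one group than in another is a statement about the difference between two treatment effects. The specified model holds the treatment odds ratio constant across groups, so it does not address that hypothesis. What it does estimate is which characteristics go with success, averaged over both arms.

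Aim 3 is meant to guide treatment choice, which makes the distinction matter. A characteristic that merely predicts doing well or badly could be reported as a predictor of effectiveness. A characteristic that truly changes the benefit may be flagged or missed, depending on how its prognostic effect and its effect on benefit combine. A significant covariate therefore cannot be attributed to either source.

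**Working it through.** Aim 3 gives no sample size, success rate, effect size or power, so there is no plan figure to reproduce. The argument is about model form. The numbers below only illustrate it.

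**Model form.** Let T be treatment (0/1) and X the factor (0/1).
- Stated model: logit p = a + bT + cX. The treatment odds ratio is exp(b) at both levels of X.
- Hypothesised quantity: logit p = a + bT + cX + dTX. The treatment odds ratio is exp(b) when X=0 and exp(b+d) when X=1. The hypothesis concerns d, which the stated model sets to zero.

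**What the stated model's factor term picks up.** Let P be the factor's odds ratio for success under standard care, and R the treatment odds ratio without the factor divided by that with it. The factor's odds ratio is P in the control arm and P/R in the treated arm. With 1:1 allocation the additive model reports roughly their geometric mean, P/√R.

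Exact population check: assume 30% control success, 40% prevalence, P=1, and treatment odds ratios of 3 without the factor and 1 with it.
- Additive model: one common treatment odds ratio of 1.99 and a factor odds ratio of 0.56 (the approximation gives 1/√3 = 0.58), although the groups do not differ under standard care.
- With the product term: treatment odds ratios of 3.00 and 1.00, ratio 0.33, and factor odds ratio 1.00.

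**How often the stated model flags the factor.** Simulation of 2,000 trials per cell, Wald test at 0.05, 1:1 arms, no other covariates, no missing outcomes. Assumed: 40% prevalence (section 4.3.6 gives this share for Bellevue patients overall, not for this cohort) and intercept -0.7, so success in controls without the factor is 1/(1+e^0.7), about 33%.

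| P | Treatment OR without / with factor | P/√R | Flagged, N=250 | Flagged, N=300 |
|---|---|---|---|---|
| 2.0 | 1.5 / 1.5 | 2.00 | 75.5% | 83.0% |
| 0.8 | 3 / 1 | 0.46 | 82.9% | 90.2% |
| 1.0 | 3 / 1 | 0.58 | 55.2% | 66.2% |
| 1.3 | 1 / 1 | 1.30 | 16.4% | 18.2% |
| 1.3 | 2 / 1 | 0.92 | 5.8% | 6.3% |
| 1.3 | 3 / 1 | 0.75 | 20.4% | 23.9% |
| 1.73 | 3 / 1 | 1.00 | 5.1% | 4.7% |

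- Row 1 has no effect modification. The interaction test rejects in 5.5% and 4.8% of trials. With a common treatment odds ratio of 2 instead of 1.5, the stated model flags 75.1% and 82.2%, and the interaction test 4.1% and 6.0%.
- For the 3-versus-1 modifier, the interaction test rejects in 53% to 58% (N=250) and 58% to 63% (N=300) across these values of P.
- At P=1.3, real modification of 2 versus 1 lowers the chance of a flag compared with no modification.
- The last row is a chosen cancellation case (1.73 ≈ √3).

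**Less favourable conditions.** Add five standardised covariates (assumed odds ratio 1.5 per SD) and outcomes missing at random in 0%, 20% or 40%. The purely prognostic factor with P=2 is still flagged in 67% to 74%, 58% to 65% and 46% to 53% of trials, against 5% to 6% for the interaction test.

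**Precision of the missing term, by hand.** N=300, 40% prevalence, 30% control success, 3 versus 1. Cell sizes are 90, 60, 90 and 60. Treated success without the factor has odds 3 × 0.30/0.70 = 1.286, so p = 0.5625.
- Variance of the log ratio of odds ratios = 1/(90×0.21) + 1/(60×0.21) + 1/(90×0.5625×0.4375) + 1/(60×0.21) = 0.053 + 0.079 + 0.045 + 0.079 = 0.257; SE = 0.507.
- Power ≈ Φ(ln 3/0.507 − 1.96) = Φ(0.21) = 58%.
- The 95% interval extends exp(1.96×0.507) = 2.7-fold either side.

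**The case against.** The plan does not exclude product terms. Aim 3 is described briefly under a general reference to multivariate models. Section 3.3 says some analyses will be modelled on another ongoing study whose protocol is not available here, and section 7.2.1 says similar analyses will be performed. Figure 3 itself cannot be seen. It is fair to call this an omission from the specified model rather than a decision against interactions. None of these places specifies a treatment-by-factor term, however, so an analyst following the text would fit the additive model.

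Much of Aim 3 is also worded loosely, as characteristics associated with success or effectiveness, and the additive model can answer that. Only the ethnicity clause clearly requires effect modification. The Asp40 clause requires it if read as response to naltrexone, which its background supports. This stands as a limit on scope.

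The strongest practical objection is power. With five covariates, the interaction test for a 3-versus-1 modifier has 47% to 54%, 39% to 45% and 31% to 35% power at 0%, 20% and 40% missing outcomes. For 2 versus 1 it has 22% to 26%, 18% to 24% and 16% to 18%. Section 7.1 concedes that naltrexone's effect has not been robust, so 3 versus 1 is large. At 10% prevalence, which matters because the plan itself reports low Asp40 rates in persons of African descent, power for 3 versus 1 is about 24% even at N=300 with complete data. All of this stands, and it is why the result must be reported as an estimate with its interval. It does not rescue the additive model: low power makes an estimate imprecise, whereas the stated model estimates something else.

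Finally, the simulation inputs are assumed. They illustrate the problem and do not measure this trial's error.

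**Conclusion.** The concern holds. The only Aim 3 model described cannot estimate the difference in effect that the section hypothesises for African American participants, nor for Asp40 on the naltrexone-response reading. That conclusion follows from the model's form and depends on no assumed number.

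The illustrative consequence is substantial in both directions. Under the stated assumptions, a purely prognostic factor is usually flagged, while a large true modifier is flagged anywhere from about 5% to 90% of the time depending on its prognostic effect. The point should be fixed but is not critical: Aim 3 is exploratory and unpowered, and the primary feasibility aim is untouched.

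**What to change.** In section 7.2.2, Aim 3:

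1. For African American ethnicity, and for OPRM1 Asp40 if genotyping is done, add a treatment-by-factor term to the stated model, one factor per model, using a single binary definition of success fixed before analysis. A joint ethnicity-and-genotype model is optional. It is the only version that would try to separate the two, which the plan suggests may be linked.
2. Report the treatment odds ratio at each level of the factor and the ratio of the two, with 95% confidence intervals, labelled exploratory. State that they describe the XR-NTX+CM package, not naltrexone alone.
3. Report odds ratios from the model without product terms as prognostic, not as predictors of effectiveness.
4. If Alcoholics Anonymous or specialty-treatment involvement is examined as a modifier, use the enrollment Form 90 value, and only describe later involvement by arm.

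The cost is SAP wording and up to two extra models. Ethnicity is already collected. Genotype depends on a laboratory not yet chosen (section 6, genomic analyses) and on funding still to be sought (section 15.1).

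The downside is wide intervals for the ratio of odds ratios. The figures are the fold either side of the estimate, for N=250 to 300:

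| Setting | 0% missing | 20% missing | 40% missing |
|---|---|---|---|
| 40% prevalence, no covariates | 2.6 to 3.1 | – | – |
| 40% prevalence, five covariates | 2.9 to 3.3 | 3.3 to 3.9 | 4.0 to 5.0 |
| 10% prevalence, five covariates | 6 to 7 | 8 to 10 | 11 to 15 |

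The N=50 pilot alone gives about 13-fold (18-fold with 20% missing) without covariates, and can say little. Non-converged fits were excluded, up to 14% of trials at 10% prevalence or N=50.

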## 7 Statistical Plan

### 7.1 Sample Size Determination

Naltrexone has not demonstrated a robust treatment effect; however, most studies did not use the XR-preparation, are limited by poor adherence, and did not include this higher-severity population or other intervention components. We do not know what the “ideal” population for XR-NTX is, but posit that it may have a greater effect size in this more severely affected population than amongst the higher socioeconomic status population historically targeted. A recent pilot of XR-NTX suggests a possible greater effect (and acceptability) in a population similar to ours. Our literature search yielded no studies of initiating pharmacotherapy for alcohol dependence in the ED. There are only limited data on XR-NTX effects on several long-term outcomes of interest, including healthcare use, treatment engagement, and quality of life measures. ED-based case management studies demonstrate promising healthcare utilization outcomes, but most were uncontrolled and overestimated effect because of regression to the mean. The heterogeneity in study designs, interventions, and cohort characteristics precludes meta-analysis.

Determining sample size is challenged by limitations in the existing data and heterogeneity of populations. Definitively testing the relative effects of intervention components may require additional arms with as many as 75 to 200 subjects in each. Thus, we chose to start with the strongest intervention and compare it to standard care to maximize the likelihood of seeing an effect and of exploring effect size on various outcomes. The 2-arm design will minimize the loss of power and allow us to focus on the primary goal of assessing feasibility.

The first phase of study will be a feasibility and acceptability study, through which we will obtain preliminary data to inform the power analysis for the subsequent definitive trial. In the first phase, we plan to pilot the study in 50 subjects. In the second phase of study, we project enrolling 125 subjects in each of the two arms to definitively test the intervention’s effect on multiple outcomes of interest. Thus, we

CONFIDENTIAL

This material is the property of the NYU School of Medicine and Langone Medical Center. Do not disclose or use except as authorized in writing by the study sponsor

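### Aim 3 ties its odds ratios to predictors that reach significance, which biases the reported estimates away from 1 (strongly in the 50-subject pilot, modestly at 250-300) and leaves hypothesised predictors without an estimate

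*Combined protocol and SAP*

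**What the plan says.** Section 7.2.2, Aim 3, describes the model: "The analysis will utilize a logistic regression with an indicator variable for treatment and covariate terms for baseline potential prognostic indicators". Six covariates are named: African American ethnicity, baseline drinking severity, housing, social support, quality of life and OPRM1 genotype. The reporting rule follows: "Odds ratios will be calculated to quantify the risk to treatment failure of significant predictors". No threshold or selection procedure defines significance. The later commitment in that section to report all endpoints concerns drinking outcomes and biomarkers, not predictors.

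Two of the six covariates carry a prior hypothesis: "we hypothesize a priori that there will be less robust effectiveness among African Americans", and "presence of the Asp40 OPRM1 SNP will be associated with treatment effectiveness". The section also says that "these analyses will be exploratory, as the study is not powered to carefully test these secondary hypotheses".

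Section 7.1 gives the sample sizes: "In the first phase, we plan to pilot the study in 50 subjects" for phase 1, then 125 per arm (250) for phase 2, and 300 in both phases. Sections 2 and 3.3 say that the Aim 3 results are meant to inform treatment choice and to allow comparison with other study populations.

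**The concern.** When power is low, an estimate reaches significance only if it lies well away from 1. Odds ratios shown because they are significant are therefore too extreme on average. A predictor that was hypothesised in advance but misses the threshold gets no estimate, although in an exploratory analysis the estimate and its interval are the result. Declaring the analysis exploratory tells the reader to be cautious; it does not undo the selection. What is at stake is the use the plan names for Aim 3: a filtered odds ratio is a poor guide to prognosis, and a missing one cannot be compared with another study.

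**Working it through.** **Inputs from the plan.** N = 50, 250 and 300 (section 7.1). Treatment plus six covariates (Aim 3). About 40% of the site's patients are African American (section 4.3.6). The plan gives no power figure for Aim 3, so there is none to reproduce. Its sample-size figures for ED visits do reproduce with a two-sided 0.05 t-test: a difference of 6 with SD 15 gives d = 6/15 = 0.40, hence 99.1 and 132.3 per arm, rounded up to the stated 100 (80% power) and 133 (90% power). I carry the two-sided 0.05 level over to Aim 3.

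**Inputs assumed.** Success rate p of 45-50%, predictor prevalence q of 20-40%, true odds ratios of 1.5, 2 and 3, no attrition. The plan gives no OPRM1 carrier rate, no success rate and no expected odds ratio for Aim 3.

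**Formula.** For a binary predictor, SE(log OR) = 1/√[N·p(1−p)·q(1−q)]. With λ = log(OR)/SE:

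- chance of passing the filter: P = [1 − Φ(1.96 − λ)] + Φ(−1.96 − λ)
- exaggeration of the log odds ratio: M = E(|estimate| given p < 0.05) / log(OR)
- smallest odds ratio that can be significant: exp(1.96·SE)

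**Worked case**, N = 50, p = 0.5, q = 0.4, OR 2. SE = 1/√(50 × 0.25 × 0.24) = 1/√3 = 0.577. λ = 0.693/0.577 = 1.20. P = 22%. The smallest significant odds ratio is exp(1.96 × 0.577) = 3.1, so a true odds ratio of 2 can pass in the right direction only by being overstated. M = 2.1.

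**Results for q = 20-40% and p = 50%.** The formula isolates the filter. The simulation fits the logistic model with seven covariates (1,500 replicates per cell, non-converged fits dropped), so at N = 50 it also contains small-sample bias.

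| N | True OR | Passes: formula | Passes: simulation | Exaggeration: formula | Exaggeration: simulation |
|---|---|---|---|---|---|
| 50 | 1.5 | 9-11% | 6-12% | 3.5-4.2 | 4.6-5.7 |
| 50 | 2 | 17-22% | 12.5-21.5% | 2.1-2.5 | 2.9-3.5 |
| 50 | 3 | 34-48% | 24-43% | 1.4-1.7 | 2.0-2.2 |
| 250 | 1.5 | 25-35% | 25-34% | 1.7-2.0 | 1.8-2.1 |
| 250 | 2 | 59-77% | 57-76% | 1.15-1.3 | 1.2-1.4 |
| 250 | 3 | 94-99% | 92-98.5% | 1.0 | 1.0-1.1 |
| 300 | 1.5 | 29-41% | 30-38% | 1.6-1.8 | 1.6-1.9 |
| 300 | 2 | 67-84% | 63-82% | 1.1-1.2 | 1.1-1.3 |
| 300 | 3 | 97-100% | 97-99% | 1.0 | 1.0-1.1 |

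At 45% success and q = 40%, the simulated exaggeration at N = 50 is 4.7 (OR 1.5) and 2.8 (OR 2). At N = 250-300 it is about 1.6-1.8 and 1.15-1.2.

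**Predictors left without an odds ratio, true OR 2.** At N = 50: 100 − 22 to 100 − 17 = 78-83% by formula, and 100 − 21.5 to 100 − 12.5 = 78.5-87.5% by simulation. At N = 300: 16-33% by formula, and 18-37% by simulation.

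**How much is the filter at N = 50.** At a true OR of 2 and q = 40%, the unfiltered mean log odds ratio is already about 26% too large, with a median odds ratio of about 2.3. Dividing it out gives 2.9/1.26 ≈ 2.3, close to the formula's 2.1. Most of the exaggeration is therefore the filter, but not all.

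**Events per parameter in the pilot.** 0.45 × 50 = 22.5 events over eight parameters (intercept, treatment, six covariates) is 2.8; at 50% success, 25/8 = 3.1.

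**The case against.** The sentence does not contain the word *only*. It does not forbid other odds ratios, and because the covariates are named in advance an omission would be visible. The plan also says openly that the analysis is exploratory and unpowered, and it separately promises, with no significance condition, to estimate associations for 12-step and specialty treatment involvement. All of that is fair, and it means that nothing is being concealed. It does not remove the point: no sentence commits to an odds ratio or interval for a named covariate that misses significance, so following the stated rule produces the selection.

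A reader might infer more than the plan supports:

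- *Several-fold exaggeration throughout the trial.* At 250-300 subjects this appears only for weak effects (true OR 1.25: 2.6-3.5 times) or for a rare predictor with a modest effect (prevalence 10%, OR 1.5: 2.4-2.6 times).
- *Overstating who benefits from treatment.* The stated model has a treatment indicator and covariate terms but no interaction. Its odds ratios describe prognosis. The hypotheses about effectiveness concern a different quantity, which reporting every odds ratio would not supply either.
- *Undermining the planning of phase 2.* Section 2 assigns preliminary effect sizes to Aim 2, and section 7.1 sizes phase 2 without using Aim 3.
- *A high chance of a spurious predictor.* With six null predictors, 1 − 0.95⁶ = 26% of analyses would show at least one. That is multiplicity, and reporting every odds ratio does not change it.

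**Conclusion.** The point holds, with its size depending on the phase. In the 50-subject pilot, the reported log odds ratios would be about 3 to 6 times too large at true odds ratios of 1.5 to 2, partly from small-sample bias, and most hypothesised predictors of that strength would receive no odds ratio. At 250-300 subjects the exaggeration is about 1.1 to 2 times, and close to none at a true odds ratio of 3. These figures rest on the assumed success rate, prevalence and true odds ratios, and on a two-sided 0.05 threshold that the plan does not state for this aim. A success rate further from 50%, a rarer predictor or attrition would make matters worse. This is a correction to an exploratory aim that should be made; it does not touch the feasibility aim or the comparison of arms.

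**What to change.** Replace the sentence on odds ratios by:

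*The model keeps all covariates named above; the odds ratio and 95% CI of every one will be reported whatever its p-value, as exploratory estimates.*

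This removes the bias due to the filter by construction. For the analysis of the 50-subject phase, add that penalised (Firth) logistic regression will be used, because there are only about 3 events per parameter and ordinary logistic estimates are themselves too large there. Two details need settling for the sentence to be applied cleanly: the covariate list is open-ended as written, and Aim 3 does not define which outcome counts as treatment success.

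The cost is a longer table in which many intervals, especially in the pilot, will be wide. No further data or subjects are needed.
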